# B. Study Type and Design:

This study is a pre-post interventional parallel randomized control trial pilot study. We will enroll 40 patients with FM to undergo QST testing on two separate days: baseline (Testing As Usual, no sound) and auditory listening. Participants will be randomized to two auditory listening conditions: music listening and nature sound listening. The conditions will be counterbalanced across subjects such that some will have listening on their first testing day and no sound on the second, and the rest of the subjects will have no sounds on the first day and listening on the second. Participants will be seated in a quiet room and a heart monitor will be attached. The participant will wear headphones during all testing sessions (including the no-sound control). They will listen to 10 minutes of the specified auditory recording (or silence) prior to QST testing. The researcher will then conduct the QST while the participant continues to listen to the auditory recording. The QST testing battery will last for approximately 1 hour. The researcher collecting QST data will be blinded to which recording the participant is hearing.

After screening, informed eConsent, and enrollment into the study, all subjects will undergo an evaluation which includes a battery of questionnaires for patient phenotyping that will assess symptoms including pain, physical function, depression, anxiety, and catastrophizing symptoms. QST parameters will also be performed after questionnaire administration as described above.

## C. Sample size, statistical methods, and power calculation

Statistical Analysis: Data analysis will be performed by the KUMC Department of Biostatistics. The data analyst will also be blinded to whether data was during the nature sounds or music listening condition. Once all data have been collected and summary scores have been calculated, the database will be locked. Only then will the blind be broken for whether the QST scores were associated with music or nature sounds, and the final statistical test will be conducted.

Aim 1 Analyses: Pain thresholds and temporal summation scores will be treated as continuous measures and normality will be assessed prior to analysis. QST data will be analyzed using a paired t-test or appropriate nonparametric test to detect changes within-subject changes in QST measures between nature sounds or music listening.

Aim 2 Analyses: Magnitude of changes in QST measures between nature sounds and music listening will be calculated and correlated to the subjective measures of pain and music that are administered via patient-reported outcome questionnaires. All measures will be treated as continuous measures and normality will be assessed prior to analysis. These relationships will be analyzed using Pearson's correlation testing.

Sample size for Study Procedures in Aims 1 and 2: It is not possible to conduct adequate power analyses for the aims as this pilot study will be the first to measure QST changes with a music listening intervention in this patient population. Sample sizes for studies included in previous meta-analyses ranged from 25 to 175. We will use the data collected in this pilot study to estimate effect sizes for the next application for a larger trial.

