#### II. SPECIFIC AIMS

Aim 1: Determine whether music listening during pain sensitivity testing has an analgesic effect on pain thresholds and tolerance and whether this effect is of greater magnitude in comparison to a non-musical auditory stimulus in patients with Fibromyalgia (FM). In order to accomplish this

Aim, patients with FM will undergo a variety of quantitative sensory testing (QST) procedures in order to KUMC – HRPP- 03/12/2015 Page 1 of 19 fully characterize their peripheral and central nervous system pain processing systems, including mechanical pain sensitivity and temporal summation. QST testing will be done at baseline (no auditory stimulus of any kind) and then will be repeated within the same subject while listening to the auditory stimulus. Patients will be randomized to either the Music arm or the Placebo (nature sounds) arm. Half of the patients will listen to music, and half will listen to nature sounds during testing. Hypothesis 1a: We hypothesize that both listening conditions will reduce pain sensitivity (lead to higher pain thresholds and tolerance) as compared to the no-sound control. Hypothesis 1b: We hypothesize that the use of music listening during QST tasks will reduce pain sensitivity as compared to the use of only nature sounds. Aim 2: Identify whether the objective analgesic effects of music listening are associated with subjective measures of anxiety, pain catastrophizing, resilience, and measures of music experience and enjoyment. In order to accomplish this Aim, the degree of analgesic effect of auditory listening (as measured by the difference in QST measures between baseline and music listening) will be calculated and correlated to subjective measures of pain and other pain-related patient characteristics using patient-reported outcome (PRO) measures. Hypothesis 2: We hypothesize that greater analgesic effect of music listening will be associated with lower levels of anxiety, depression, and with higher levels of music experience and enjoyment.

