Randomization Procedures: Participants will be randomized following eConsent using the REDCap Randomization tool. Randomization is defined using a random number generator, and stratified by gender to ensure equal numbers of males and females in each group. Audio files will be labelled with dummy codes to blind the researcher collecting the data. A file will also be created for the no-sound condition, to further keep the researcher blinded.

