Music and sound delivery: Auditory stimuli will be presented using an iPod and Bluetooth noise-cancelling headphones. Listening will begin 10 minutes prior to QST and will continue for the duration of the QST, for a total of 1 hour and 10 minutes. The listening condition will be a single bout on one of two days of testing. This is a two-arm parallel design RCT with Testing as usual (no-sound) and placebo control (nature sounds).

Heart Monitoring: Subject's electrocardiogram (ECG) will be recorded with a measurement device (Biopac/AcqKnowledge software) that consists of a computer-operated recording device and amplifier. The recording device and amplifier are attached to standard snap-on ECG electrodes. Three ECG electrodes are placed: one under the collar bone, one under the rib cage on the opposite side, and a ground on the abdomen. ECG will be recorded throughout each testing session. The time of each condition (passive listening vs. active listening with sensory/pain stimulus) will be recorded by the investigator. The ECG will be uploaded to Kubios software for analysis. Metrics of heart rate and variability in time-, frequency, and non-linear domains will be compared between conditions (passive vs. active listening) and between sounds (nature sounds vs. music).

Music characteristics: The musical selections will be professional recordings of instrumental Classical music selected by the researcher (See Appendix 1). All participants will hear the same pieces in the same order. Instrumentation ranges from piano solo to full orchestra, but they are without lyrics or heavy percussion. Pitch ranges across the pieces, but is standard across participants and not controlled by either the participant or the researcher. Tempo for all of the pieces is slow (~60 beats per minute). The pieces are in either major keys or minor keys, but all consist primarily of consonant harmonies and sustained melodic phrases. Participants will control the volume to their individual comfort level.

Placebo control: Professional recordings of nature sounds selected by the researcher without added music will be used as the active placebo control condition. All participants will hear the same recording. This active control condition will allow for non-musical analgesic effects, such as distraction, to be controlled in the experimental design. Participants will control the volume to their individual comfort level.

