Mitigation of bias: We propose to use several strategies to mitigate potential bias in this study. Participants will be randomized to experimental or placebo group, group allocation will be concealed from personnel and they will be blinded throughout testing and analysis. Patients cannot be blinded as they will know whether they are hearing nothing, music, or nature sounds during testing. Our counterbalancing of testing days will help to ensure that attrition is not affecting one condition to a greater degree than another. Finally, our strategy to avoid potential publication bias is that by having both a no-sound control and a placebo nature sound control, we will be able to determine whether a) there is an analgesic effect of distraction in this population, and b) whether that effect is greater for music over another distracting auditory stimulus.

Study Limitations and Plans to Overcome Them: Recruitment: We do not anticipate that there will be any difficulty with participant recruitment. Given the clinically significant volume of fibromyalgia patients seen at the [name], Comprehensive Spine Center, we are confident that subject enrollment will be achievable within the allotted timeframe. Also, we plan on using the innovative recruitment programs available at KUMC to assist investigators with participant recruitment including the Frontiers Registry and the Pioneers Community

Research Recruitment Registry. Our project budget includes a financial incentive for patient participation which will aid in recruitment and compliance with study procedures.

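### Aim 1 names only a paired within-subject test, but music versus nature sounds is a between-subject factor, so Hypothesis 1b has no correctly specified test

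*Combined protocol and SAP*

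**What the plan says.** Specific Aims sets the allocation: "Half of the patients will listen to music, and half will listen to nature sounds during testing". Section II.B confirms it: "Participants will be randomized to two auditory listening conditions: music listening and nature sound listening". Under Music and sound delivery, exposure is limited to one session per person: "The listening condition will be a single bout on one of two days of testing". The other day is no-sound, and the order of the two days is counterbalanced.

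Hypothesis 1a compares listening with no sound. Hypothesis 1b states that music "will reduce pain sensitivity as compared to the use of only nature sounds". The Mitigation of bias paragraph says the study will establish "whether that effect is greater for music over another distracting auditory stimulus".

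Section II.C gives one Aim 1 method, a "paired t-test or appropriate nonparametric test to detect changes within-subject changes in QST measures between nature sounds or music listening". It adds that the blind to music or nature sounds is broken after database lock and that a final test follows, but it does not say which test. Its Aim 2 paragraph correlates questionnaire scores with a change from nature sounds to music. Specific Aims defines the Aim 2 effect differently: "as measured by the difference in QST measures between baseline and music listening". Section V.A adds only when analyses will be done. The heart-monitoring text compares sounds for ECG metrics, not QST, and names no test.

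**The concern.** A paired test needs two values from the same person. Here the two sounds are heard by different people, so the method and the contrast attached to it do not fit the design. Hypothesis 1b asks whether music does more than distract, and the nature-sound arm exists to answer that. If the named test is followed, 1b is either tested on undefined pairs or not tested at all.

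Two consequences follow. The arm comparison would have to be chosen after the blind is broken. And although the pilot is meant to supply effect sizes for a larger trial, the one that trial would need for 1b, the between-arm difference in change with its interval, is not named as an output.

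**Working it through.** The plan states no power, effect size, SD or between-session correlation, so there is no figure to reproduce. The structural check comes first. The calculations after it only show scale.

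**Does the named test fit the data?** Each person contributes one no-sound value and one listening value. The listening value is music for about 20 people and nature sounds for about 20. Participants with both a music and a nature-sound value: 0 of 40.

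- *Literal reading (music paired with nature sounds):* there are no natural pairs and no pairing rule.
- *Charitable reading (listening versus no-sound within arm):* valid for 1a, but it gives no estimate or test of the arm difference.
- *The nonparametric alternative:* it is offered in place of the paired t-test and aimed at the same within-subject change, so it does not supply a between-arm test.

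**Inputs for the illustrations.** From the documents: N = 40, split in half, so 20 per arm. Assumed: two-sided alpha 0.05, no dropout, normal data, and the effects and correlations shown.

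**(1) Judging 1b from within-arm significance.** The plan does not propose this, but within-arm tests are all the charitable reading provides. Here the effect is in SDs of the within-person change (dz). Power p of a paired t-test with n = 20 uses noncentrality dz × √20 on 19 df. If both sounds work equally well, the chance that music alone is significant is p(1 − p).

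| dz | p | p(1 − p) |
|---|---|---|
| 0.2 | 0.136 | 0.117 |
| 0.3 | 0.247 | 0.186 |
| 0.45 | 0.480 | 0.250 |
| 0.5 | 0.565 | 0.246 |
| 0.6 | 0.721 | 0.201 |
| 0.8 | 0.924 | 0.070 |
| 1.0 | 0.989 | 0.011 |

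A two-sided between-arm test would favour music in 0.05 / 2 = 2.5% of such trials.

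**(2) Pairing unrelated participants.** From here on the effect is in SDs of a single session's value. A pairing fixed in advance keeps type I error near 5% (simulated 4.9% to 5.1%), but none is given. In 1,000 simulated datasets with 500 random pairings each, a verdict was called pairing-dependent if p < 0.05 and p ≥ 0.05 each occurred in more than 2.5% of pairings. That held in 9%, 19%, 32% and 34% of datasets at music advantages of 0, 0.3, 0.5 and 0.7 SD.

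**(3) Power for a 0.5 session-SD music advantage, 20 per arm.** Let r be the between-session correlation.

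- Arbitrary pairing: noncentrality 0.5 × √10 = 1.581 on 19 df, power 0.324 at any r.
- Change scores: SD √(2(1 − r)), noncentrality 1.581 / √(2(1 − r)) on 38 df.
- ANCOVA on the no-sound value: residual SD √(1 − r²), noncentrality 1.581 / √(1 − r²) on 37 df. The simulated column (40,000 runs per setting) also adjusts for order and gender.

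| r | Arbitrary pairing | Change scores | ANCOVA, formula | ANCOVA, simulated |
|---|---|---|---|---|
| 0.3 | 0.324 | 0.256 | 0.365 | 0.354 |
| 0.5 | 0.324 | 0.338 | 0.428 | 0.419 |
| 0.7 | 0.324 | 0.512 | 0.578 | 0.565 |
| 0.8 | 0.324 | 0.683 | 0.728 | 0.716 |

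Raw change scores do worse than arbitrary pairing below about r = 0.47. ANCOVA has the highest power at all four values of r.

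**(4) Precision of the missing estimate.** With change scores, the 95% CI half-width for the arm difference is 2.024 × √(2/20) = 0.64 SD of the change.

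**The case against.** The intent is visible. The plan breaks the blind between music and nature sounds just before a final test, it commits elsewhere to a music-versus-nature answer, and a biostatistics department will do the analysis. On this view the sentence is loose drafting in an unpowered pilot, and the data allow the right test whatever the text says. This is fair as to intent. It does not supply a method: no between-arm QST test is named anywhere, and the same wrong contrast recurs in the Aim 2 paragraph. Pilot status explains the missing power calculation, not a test that does not match the design.

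The objection to the numbers has more force. Illustrations (1) and (2) measure procedures the plan does not state, and pairing strangers is an unlikely way to run the analysis. The literal reading costs little on average: type I error holds, and at r = 0.5 power is 32% against 34% for change scores. The pairing-dependence rate also varies with its cut-off: a separate simulation of 600 datasets at 0.5 SD gave about 31%, 27% and 23% at cut-offs of 2.5%, 5% and 10%. These figures are illustrative, and the finding does not rest on them.

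Finally, ANCOVA is not the only cure. A two-sample comparison of change scores, or a mixed model with an arm-by-condition term, would also test 1b. That stands; ANCOVA is preferred for its power, not because it is the only valid choice.

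**Conclusion.** The concern holds and should be fixed before unblinding. That 0 of 40 participants supply a music/nature pair follows from the design alone, with no assumption about effects. The paired test suits 1a. Hypothesis 1b has no correctly specified test, although every participant has a no-sound and a listening value and arm is randomised.

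The numerical consequence depends on what the analyst would do instead. If within-arm significance were used and the sounds were equally effective, music alone would be credited in 1% to 25% of trials over dz = 0.2 to 1.0, highest near 0.45 to 0.5 and below the 2.5% benchmark only at the top of that range. If a proper between-arm test were used, power for a 0.5 session-SD advantage would be about 26% to 68% with change scores and 35% to 72% with adjusted ANCOVA, for r from 0.3 to 0.8. All of this assumes 20 per arm, normal data, two-sided 0.05 and no dropout. The 10 kg/cm2 pressure ceiling and the ratio form of the wind-up measure were not modelled.

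**What to change.** Replace the Aim 1 sentence in section II.C with two specifications.

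- **Hypothesis 1a:** paired t-test, or Wilcoxon signed-rank test, of listening versus no-sound within each arm.
- **Hypothesis 1b:** ANCOVA of the listening-session value on arm, adjusted for the no-sound value, session order (counterbalanced by design) and gender (randomisation is "stratified by gender to ensure equal numbers of males and females in each group"). If model assumptions fail, use a rank-sum test comparing within-person change (listening minus no-sound) between arms, accepting that raw change is less efficient when r is low. Report the between-arm difference with its 95% CI, and state that within-arm p-values will not be used to judge 1b.

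In the Aim 2 paragraph, replace the music-versus-nature change with the no-sound-to-listening change that Specific Aims describes. State whether the correlations use the music arm only (about 20, as the wording of Hypothesis 2 suggests) or all 40, since Specific Aims refers to both auditory listening and music listening.

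The cost is one paragraph for Aim 1 and a sentence or two for Aim 2. No new data, visits or participants are needed.

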This two-arm parallel randomized controlled pilot study will enroll 40 patients with fibromyalgia. Patients' pain thresholds and sensitivity will be measured using a battery of quantitative sensory tests (QST). All patients will have two testing sessions: one under testing as usual conditions with no-sound, and one while listening to either instrumental Classical music, selected by the researchers with careful consideration of the musical characteristics, or a nature sound placebo control condition. This careful experimental design will allow us to test whether music listening elicits greater analgesic effects over simple auditory distraction. To minimize potential bias we will employ sound cancelling headphones and randomization of conditions so that the researcher collecting the QST measures will be blinded to whether the patient is hearing music, nature sounds, or nothing. The proposed study is significant as it will identify whether music listening has an analgesic effect during pain threshold and tolerance testing for patients with FM that supersedes any effect of auditory distraction. Results from the proposed study may provide objective evidence that music listening objectively improves analgesia and pain management and thus could be considered therapeutic during situations where acute pain is expected

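### The Aim 2 analysis correlates a within-person music-versus-nature change that no participant will have, and it conflicts with the score defined in the Specific Aims

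*Combined protocol and SAP*

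**What the plan says.** The Aim 2 paragraph of section II.C reads: "Magnitude of changes in QST measures between nature sounds and music listening will be calculated and correlated to the subjective measures". It goes on to name Pearson's correlation as the method.

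The Specific Aims define the score differently. Aim 2 there speaks of "the degree of analgesic effect of auditory listening" and measures it as the "difference in QST measures between baseline and music listening", where baseline is the no-sound session. Hypothesis 2 concerns the analgesic effect of music listening.

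The design is described consistently elsewhere:

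- Abstract: "All patients will have two testing sessions: one under testing as usual conditions with no-sound, and one while listening to either instrumental Classical music", or to nature sounds.
- Specific Aims, Aim 1: "Half of the patients will listen to music, and half will listen to nature sounds during testing".
- Music and sound delivery: "The listening condition will be a single bout on one of two days of testing".
- Section II.B: "Participants will be randomized to two auditory listening conditions: music listening and nature sound listening". The counterbalancing concerns only the order of listening and no-sound: "some will have listening on their first testing day and no sound on the second", and the reverse for the rest.

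**The concern.** A Pearson correlation needs one value of each variable per person. The variable named in II.C requires the same person to be tested under both music and nature sounds, and the design never does this. The sentence therefore cannot be carried out as written.

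It also uses a different reference condition (nature sounds) from the Specific Aims (no sound). Whoever runs the analysis must substitute something: the music arm alone, both arms pooled, or both arms adjusted for arm. These estimate different things. Under II.C the music/nature blind is broken before the final test, so an unresolved definition could be settled with allocation known. The pilot's effect sizes are meant to inform a larger trial, so an unclear definition would carry forward.

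**Working it through.** The plan gives no power calculation or other figure for Aim 2, so there is none to reproduce. The check is a count from the design.

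**Who has which score.** Inputs: 40 participants (Abstract); two sessions each, one without sound (Abstract); half allocated to each sound (Specific Aims); one listening bout each (Music and sound delivery).

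| Pair of conditions in the same person | Participants |
|---|---|
| Nature sounds and music (II.C, Aim 2) | 0 of 40 |
| No sound and music (Specific Aims, Aim 2) | 40 / 2 = 20 |
| No sound and nature sounds | 40 / 2 = 20 |
| No sound and either sound | 20 + 20 = 40 |

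The zero does not depend on the exact split. The 20 and 40 are design counts before any dropout.

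**Can the text be read another way?** Suppose II.C means each person's change from no sound, compared between arms. That comparison yields one arm difference per QST measure, with no variation between people, so it has no correlation with a questionnaire. The Aim 2 sentence does not mention the no-sound session at all.

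The remaining figures concern the replacement analysis only.

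**Precision.** By Fisher's z, the 95% interval is tanh(atanh(r) ± 1.96/√(n − 3)), with n − 4 when one covariate is partialled out. For an observed r = 0.3 and n = 20, atanh(0.3) = 0.310.

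- Unadjusted: 1.96/√17 = 0.475, so tanh(−0.166) to tanh(0.785), which is −0.16 to 0.66.
- Adjusted for session order: 1.96/√16 = 0.490, so tanh(−0.180) to tanh(0.800), which is −0.18 to 0.66.

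**Number of correlations.** Four QST measures (threshold, tolerance, PAIN50, wind-up ratio) by five scores (anxiety, depression, catastrophizing, Brief MEQ, liking) gives 4 × 5 = 20. This assumes that the Brief MEQ gives a single total and that no separate pain score is added. At an assumed 5% level, 20 × 0.05 = 1 would be expected to be nominally significant if no association were real.

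**Pooling the arms without an arm term.** Assume equal arms, no correlation within either arm, and both variables higher by d within-arm SDs in the music arm. The pooled correlation is then r = 0.25d²/(1 + 0.25d²).

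| d (assumed) | Calculation | Pooled r |
|---|---|---|
| 0.5 | 0.0625/1.0625 | 0.06 |
| 0.8 | 0.16/1.16 | 0.14 |
| 1.0 | 0.25/1.25 | 0.20 |

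**The case against.** The strongest reply is that this is loose drafting with little harm. A computable score already stands in the Specific Aims of the same document, no data are lost, and this is the second aim of an unpowered pilot. The neighbouring Aim 1 sentence joins the two sounds with *or*, which suggests that the no-sound comparator was simply left out. That may well be the cause, and it limits the seriousness. It does not make the Aim 2 sentence runnable or remove the conflict with the Specific Aims.

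A second reply is that nothing ranks the Specific Aims above II.C, and the Abstract stresses an effect of music beyond distraction. Whether a questionnaire score modifies the music-over-nature effect could be studied with an arm-by-score interaction. That is a legitimate question and a more direct check of music-specificity than two correlations side by side. But it is not the correlation that II.C describes, and Hypothesis 2 as worded concerns the effect of music listening.

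Third, the pooling figures apply only when the questionnaire score also differs by arm. This stands. The phenotyping questionnaires precede QST, so randomisation makes their expected arm difference about zero. The caution mainly concerns the liking rating, which refers to the assigned sound.

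Finally, 20 and 40 are upper limits if participants drop out between visits, and the count of 20 correlations rests on the assumptions stated with it. Neither affects the main finding.

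**Conclusion.** The concern holds. The score named for Aim 2 in II.C exists for 0 of 40 participants and contradicts the definition in the Specific Aims. This follows from the design text alone and needs no numerical assumption. The Specific Aims score exists for about 20 participants, and a listening versus no-sound difference exists for all 40, both before dropout.

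The text should be corrected, but the defect is not fatal. Hypothesis 2 remains testable from planned data once the score and the analysis population are stated.

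**What to change.** Replace the Aim 2 sentence in II.C before the music/nature blind is broken:

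- **Score.** Use each participant's own listening versus no-sound difference, signed so that positive means analgesia: listening minus no sound for threshold, tolerance and PAIN50; no sound minus listening for the wind-up ratio. Calculate it with the other summary scores before database lock. It does not require knowing which sound was played.
- **Hypothesis 2 result.** Report music-arm correlations (n about 20) with 95% intervals for anxiety, depression, music experience and enjoyment, and for catastrophizing, which Aim 2 also names. State whether enjoyment means the liking rating, the Brief MEQ or both, and name any pain score to be included. Label the whole set as exploratory estimation.
- **Method.** Adjust for session order, and use Spearman's correlation where the planned normality check fails.
- **Nature-sound arm.** Report the same correlations alongside as an exploratory check of music-specificity. If effect modification is the real interest, specify an arm-by-score interaction, also exploratory.
- **Both arms together.** If this estimate is given, label it secondary and adjust it for arm.

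Align the Aim 1 sentence in the same edit: listening versus no sound within person for Hypothesis 1a, and a between-arm comparison of those differences for Hypothesis 1b.

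The cost is wording only, with no change to randomisation, visits, QST or questionnaires. The drawback is low precision, which is acceptable in a pilot meant to estimate effect sizes.

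A minor separate point: Aim 2 names resilience, but no listed questionnaire measures it. Either delete it from the aim or add a few items.
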